## 6.5.2. Functional Antibody Titers Fold Increase

#### Definition

The fold increase of the functional antibody response will be calculated for all post-baseline time points as post-dose value / baseline value.

## Analysis

The fold increase in functional antibody titers will be summarized using descriptive statistics for all post-baseline time points. Additionally, GMFR with 95% CI will be presented.

Functional antibody titers fold increase will be listed.

Figure: The fold increase of functional antibody titers will be presented graphically displaying GMFR with 95% CI at all time points (line plot).

## 6.5.3. Seroconversion

#### Definition

Seroconversion is defined as a minimum of 4-fold increase of functional antibody response as compared to baseline.

#### Analysis

The number of subjects with seroconversion will be summarized by number and percentage with 95% confidence interval for all post-baseline time points. The denominator of the percentages will be the number of subjects with data available at the respective visit.

Seroconversion data of the functional antibody titer will be listed.

## 6.6. Exploratory Analyses

Exploratory analyses will be described in a separate biomarker SAP provided by BioNTech.

## 6.7. Further Safety Analyses

Hereinafter, the further safety analyses for Part A are described. All analyses will be performed in the SAF.

Safety data that will be presented includes IMP compliance, clinical laboratory assessments, vital signs, and Electrocardiograms (ECGs).

#### 6.7.1. Compliance

IMP compliance will be summarized by group (i.e. by vaccine type and cohort) and cohort-total.

Drug exposure will be listed.

#### 6.7.2. Laboratory Assessments

#### Definition

Clinical laboratory data to be summarized includes hematology, clinical chemistry, and urinalysis and will be assessed at the time-points indicated in Table 5, 6 and 7 of the protocol.

The following clinical laboratory variables will be assessed:

#### Hematology

Hemoglobin, hematocrit, red blood cell count, white blood cell count and differential (neutrophils, lymphocytes, monocytes, eosinophils, basophils), platelet count.

#### Clinical chemistry

Alkaline phosphatase, creatinine, ferritin, C-reactive protein, albumin, alanine aminotransferase, amylase, aspartate aminotransferase, gamma glutamyl transpeptidase, total bilirubin, blood urea nitrogen, glucose, lipase, sodium, potassium, calcium.

Follicle-stimulating hormone: In women only.

#### Urinalysis

Dipstick: glucose, bilirubin, ketone, specific gravity  $(1 \text{ mL} \triangleq 1 \text{ g})$ , blood, pH, protein, urobilinogen, nitrite, and leukocytes.

Microscopic urinalysis: If warranted by dipstick results, urine sediment will be microscopically examined for presence of red blood cells, white blood cells, casts, crystals, epithelial cells, and bacteria.

All laboratory tests are classified as normal or lower or higher than reference range (abnormal). All abnormal laboratory tests will be classified by the investigator as clinically significant (CS) or not (NCS).

Abnormal lymphocytes data will be categorized as defined in table 15 in the protocol as grade 1 (mild), grade 2 (moderate), grade 3 (severe) and grade 4 (potentially life threatening).

#### Analysis

Clinical laboratory variables at each time-point and its change from baseline to each postbaseline time-point (for continuous variables) will be summarized using descriptive summary statistics for each parameter by group and cohort-total.

Number and percentage of subjects with low, normal and high clinical laboratory values at each time-point will be summarized for each parameter by group and cohort-total. The same table will be provided for the grading scheme (grades mild, moderate, severe and life threatening) for lymphocytes.

The number and percentage of subjects with CS abnormal, abnormal (not CS), normal and missing values will be summarized for each parameter by group and cohort-total.

Clinical laboratory values for each parameter will be summarized using shift tables from baseline to worst post-baseline value with respect to reference range values (low, normal, high) by group. Worst post-baseline might be in both directions. Each subject may be counted in the parameter high and in the parameter low category. A subject will only be counted in the normal category if

all post-baseline values are normal. If several post-baseline values are considered as worst post-baseline value, the first one is taken.

All clinical laboratory data will be presented in the data listings along with normal ranges Abnormal clinical laboratory values will be flagged in the listing.

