#### **Clinical laboratory parameters**

The clinical laboratory parameters to be summarized and assessed are listed in Section 10.2. The scheduled time points for assessment are given in the SoA (see Section 1.3).

Clinical laboratory parameters at each time point and change from baseline to each postbaseline time point will be summarized using descriptive summary statistics for each parameter by group.

Shift tables from baseline to worst intensity grade will be provided for each laboratory parameter by group.

Additionally, the occurrence of clinically significant abnormal laboratory results within a trial subject will be analyzed using descriptive summary statistics for each parameter and visit by group.

Abnormal laboratory results will be graded using criteria based on the guidance given in US FDA Guidance for Industry "Toxicity Grading Scale for Healthy Adult and Adolescent Volunteers Enrolled in Preventive Vaccine Clinical Trials" (see Section 10.3.1.11).

Laboratory parameter results will be listed along with the normal ranges. Values that are below or above the normal ranges will be flagged.

Clinical laboratory analysis details will be described in the SAP.

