#### Laboratory abnormalities

Laboratory abnormalities will be graded according to the grading scheme given in Table 14.

Table 14:	Laboratory	abnormality	grading scale
-----------	------------	-------------	---------------

Hematology	Mild (Grade 1)	Moderate (Grade 2)	Severe (Grade 3)	Potentially life- threatening (Grade 4)
Hemoglobin (female) - g/dL	11.0 – 12.0	9.5 – 10.9	8.0 - 9.4	<8.0
Hemoglobin (female) change from baseline value - g/dL	Any decrease – 1.5	1.6 – 2.0	2.1 – 5.0	>5.0
Hemoglobin (male) - g/dL	12.5 – 13.5	10.5 – 12.4	8.5 – 10.4	<8.5
Hemoglobin (male) change from baseline value - g/dL	Any decrease – 1.5	1.6 – 2.0	2.1 – 5.0	>5.0
WBC increase - cells/mm 	10,800 - 15,000	15,001 – 20,000	20,001 - 25,000	>25,000
WBC decrease - cells/mm 	2,500 - 3,500	1,500 - 2,499	1,000 – 1,499	<1,000
Lymphocytes decrease - cells/mm 	750 – 1,000	500 – 749	250 – 499	<250
Neutrophils decrease - cells/mm 	1,500 – 2,000	1,000 – 1,499	500 – 999	<500
Eosinophils - cells/mm 	650 – 1,500	1,501 – 5,000	>5,000	Hypereosinophilic
Platelets decrease - cells/mm 	125,000 - 140,000	100,000 - 124,000	25,000 - 99,000	<25,000
Chemistry	Mild (Grade 1)	Moderate (Grade 2)	Severe (Grade 3)	Potentially life- threatening (Grade 4)
BUN - mg/dL	23 – 26	27 – 31	>31	Requires dialysis
Creatinine - mg/dL	1.5 – 1.7	1.8 – 2.0	2.1 – 2.5	>2.5 or requires dialysis
Alkaline phosphatase - increase by factor	1.1 – 2.0x ULN	2.1 – 3.0x ULN	3.1 – 10x ULN	>10x ULN
Liver function tests - ALT, AST - increase by factor	1.1 – 2.5x ULN	2.6 – 5.0x ULN	5.1 – 10x ULN	>10x ULN
Bilirubin - when accompanied by any increase in liver function test - increase by factor	1.1 – 1.25x ULN	1.26 – 1.5x ULN	1.51 – 1.75x ULN	>1.75x ULN
Bilirubin - when liver function test is normal - increase by factor	1.1 – 1.5x ULN	1.6 – 2.0x ULN	2.0 – 3.0x ULN	>3.0x ULN

Abbreviations: ALT = alanine aminotransferase; AST = aspartate aminotransferase; BUN = blood urea nitrogen; ULN = upper limit of normal; WBC = white blood cell.

BioNTech SE	Clinical Trial Protocol	Page 102 of 113
	including Amendments Nos. 01 to 09	Version: 13.0
Confidential	BNT162-01	Date: 12 JAN 2022

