		Only local and systemic reactions assessed by subject as in the diary will be analysed as primary endpoint. As additional analyses, the local and	Reactions assessed by the

		systemic reactions assessed by the investigator will also be included in tables displaying "worst possible grade" for data completeness.	investigator should also be included in the analysis.
		-TEAEs occurring in the time intervals including 7 days after each immunization will not be analyzed separately	Updated AE analysis
		- related TEAEs after 28 days after last dose are included in one of the analyzed time intervals	
		-TEAEs with DLT and deaths will be analyzed	
		- Removal of solicited reacto TEAEs that came from diary from the unsolicited TEAEs	
		Table of laboratory data by grades will only be done for lymphocytes	The table will be most useful for lymphocytes.
		References to mock tables were removed	
6	18AUG2021	Change in local and systemic reaction table	Updated reactogenicity analysis
		Clarification on assignment of Aes to time intervals and on the baseline definition	Clarifications
7	11APR2022	Update to protocol version 13.0.	New protocol version
		Data assessed after the vaccination with a non-trial SARS-CoV-2 vaccine will be excluded from all statistical analyses.	Adaptation to ongoing COVID-19 pandemic
8	01SEP2022	Added AE table	Additional table necessary for report
		Clarification on exclusion of data assessed after the vaccination with a non-trial vaccine	Clarification
9	110CT2022	Corrected numbering of section 1.3	Correction

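### The SAP drops the protocol's baseline-to-worst-grade laboratory shift tables and grades only lymphocytes, and Appendix 1 does not record the change

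*SAP*

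**What the plan says.** Protocol 9.4.5 (Clinical laboratory parameters) makes two commitments. The first is on grading: "Abnormal laboratory results will be graded using criteria based on the guidance given in US FDA Guidance for Industry". The second is on presentation: "Shift tables from baseline to worst intensity grade will be provided for each laboratory parameter by group". Protocol 10.3.1.11 names the scale: "Laboratory abnormalities will be graded according to the grading scheme given in Table 14". The same part of 9.4.5 also leaves room for elaboration: "Clinical laboratory analysis details will be described in the SAP".

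SAP 6.7.2 plans something different. Its shift tables use another classification: "Clinical laboratory values for each parameter will be summarized using shift tables from baseline to worst post-baseline value with respect to reference range values", that is, low, normal or high. The only graded output follows on from the table of low, normal and high counts at each time point: "The same table will be provided for the grading scheme (grades mild, moderate, severe and life threatening) for lymphocytes". The definition behind it is equally narrow: "Abnormal lymphocytes data will be categorized as defined in table 15 in the protocol".

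The restriction is deliberate. The SAP Version History entry for version 5 (13 July 2021) reads: "Table of laboratory data by grades will only be done for lymphocytes". The reason given is that the table is most useful for that test. The SAP introduction says that changes from the protocol are documented in Appendix 1 (Section 7.1). Appendix 1 lists changes to the adverse event and reactogenicity analyses and has no laboratory entry.

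**The concern.** The two current documents promise different analyses of the same data, and the one that will be programmed gives less. Describing safety is the trial's primary objective, and severity grade is what separates a trivial laboratory change from a serious one. Grade also matters in the conduct of the trial: protocol 6.6.1 counts clinically significant laboratory abnormalities of Grade 3 or higher towards one of its dose-limiting-toxicity criteria.

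Low, normal and high categories do not carry grade. On the Table 14 scale, an ALT of 1.1 times the upper limit of normal is Grade 1 and an ALT above 10 times that limit is Grade 4. Both are simply high.

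The change could also pass unnoticed. Protocol 9.4 asks the trial report to justify deviations from the final SAP. Because the SAP itself omits the analysis, following the SAP would not count as a deviation.

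**Working it through.** No stated figure has to be reproduced. The check is a comparison of texts and a count.

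**Step 1: the texts side by side**

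| Question | Protocol 9.4.5, 10.3.1.11 | SAP 6.7.2 |
|---|---|---|
| Which tests are graded? | Abnormal results, on the Table 14 scale | Lymphocytes |
| What does the shift table classify? | Worst intensity grade | Low, normal, high |
| What form does the graded table take? | Baseline to worst, per parameter | Counts at each time point |

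The lymphocyte table does not link a subject's baseline grade to the worst later grade. So the promised grade-shift table is planned for no test, lymphocytes included.

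**Step 2: the count**

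- Routine blood tests in protocol 10.2: 10 haematology + 16 chemistry = 26. FSH and urinalysis are not counted.
- Tests with a grade in Table 14: 6 haematology (haemoglobin, WBC, lymphocytes, neutrophils, eosinophils, platelets) + 6 chemistry (BUN, creatinine, ALP, ALT, AST, bilirubin) = 12. A test with several rows counts once; ALT and AST share a row and count as two.
- Tests with no grade in Table 14: 26 − 12 = 14 (haematocrit, red cell count, monocytes, basophils, ferritin, CRP, albumin, amylase, GGT, glucose, lipase, sodium, potassium, calcium).
- Gradable tests that the SAP does not grade: 12 − 1 = 11.
- Gradable tests with a grade-shift table in the SAP: 0 of 12.

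**Step 3: what the remaining tables show for the 11 tests**

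- *Descriptive statistics* (SAP 6.1.1 and 6.7.2) give the minimum and maximum per parameter, time point and group. An extreme value would show, but not how many subjects reached a grade or where they started.
- *Clinical-significance counts* (SAP 6.7.2) split abnormal values by investigator judgement. Table 14 mostly uses numeric thresholds, so the two classifications need not agree.
- *TEAEs by worst grade and TEAEs of Grade 3 or higher* (SAP 6.4.3) include laboratory abnormalities reported as adverse events. Protocol 10.3.1.7 says that findings judged not clinically significant should not be recorded as AEs. Protocol 10.3.1.9 says that where an abnormality is a sign of a disease, or causes symptoms without a diagnosis, only the diagnosis or the symptoms are recorded. The AE grade is then not necessarily the laboratory grade.

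So an abnormality in one of the 11 tests that is judged not clinically significant is graded in no table.

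**Step 4: whether the scale can be programmed as printed**

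- The SAP cites a protocol Table 15. The protocol's list of tables ends at Table 14, which is the laboratory scale.
- Bilirubin with normal liver function tests: Grade 2 is 1.6 to 2.0 times ULN and Grade 3 is 2.0 to 3.0 times ULN, so exactly 2.0 falls in both.
- Platelets: Grade 1 starts at 125,000 and Grade 2 ends at 124,000, so a count strictly between them has no grade. This matters only if counts are reported more finely than the nearest thousand.

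**The case against.** The strongest reply has four parts.

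**The protocol delegates laboratory detail to the SAP.** It does. But protocol 9.4 describes the SAP as a more technical and detailed account of the analyses in that section. That covers how to build the table; it does not cover removing it without saying so.

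**The protocol's promise could not be met literally.** This stands for the 14 tests without a Table 14 grade. A reader might infer that severity is lost for every test other than lymphocytes. The documents do not support that, because for those 14 the protocol defines no grade to lose. The SAP's reference-range shift is a sensible display for them.

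**Severe values would still be seen.** This stands in part. A reader might infer that a Grade 4 value cannot be distinguished from a Grade 1 value in any summary table, or that it would appear only in listings. Neither follows. In a cohort of 12, an extreme value would often be the reported minimum or maximum. A clinically significant one should also appear in the clinical-significance counts, and in the graded TEAE tables if it is recorded as an AE. What is lost is the count of subjects by grade and the link to baseline.

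**The choice was open and reasoned.** The Version History dates it and gives a reason. A reader might infer selective reporting, because the choice was made during an open-label trial that allowed snapshot analyses. No text shows that graded results were examined or that they drove the decision, and all tests keep the same reference-range, change-from-baseline and clinical-significance summaries. The supported criticism is a one-line rationale and a missing Appendix 1 entry.

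Laboratory data are also not a primary endpoint. Both documents place them among the other or further safety analyses, which limits the weight of the point.

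**Conclusion.** The discrepancy is real and is in current text. SAP 6.7.2 provides a grade-shift table for none of the 12 tests that Table 14 grades, and a graded table of any kind for one. Subjects therefore cannot be counted by toxicity grade for the other 11, nor by shift from baseline to worst grade for any of the 12. Other tables cover part of the gap, but not abnormalities in the 11 that are judged not clinically significant.

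The conflict has also persisted. Protocol version 13.0 (12 January 2022) kept the commitment about six months after SAP version 5 dropped it. SAP version 7 (11 April 2022), the update to that protocol, left both the analysis and Appendix 1 unreconciled on this point.

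This is a reporting gap worth closing. It does not threaten the primary endpoints. The conclusion assumes that Table 14 is the intended scale despite the SAP's citation of Table 15, and that no separate document adds graded laboratory tables.

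**What to change.** 1. In SAP 6.7.2, restore shift tables from baseline to worst post-baseline grade, by group, for all 12 Table 14 tests. Specify how the two haemoglobin scales (absolute value and change from baseline) and the two bilirubin scales are displayed. The haemoglobin change scale has no baseline grade, so only a worst post-baseline grade can be shown for it.
2. Keep the reference-range shift tables for the 14 routine blood tests without a grade.
3. List any departure from protocol 9.4.5 that remains in Appendix 1, with its reason. This includes stating that the 14 ungraded tests cannot have a grade shift.
4. Correct the Table 15 citation to Table 14.
5. Before programming, have the sponsor reconcile the Table 14 boundaries for bilirubin at 2.0 times ULN and for platelets between 124,000 and 125,000.

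The cost is a set of standard tables. The SAP produces separate tables for five vaccine types, so one table per test would mean up to 12 × 5 = 60, or fewer if tests are stacked. The programming repeats across types and uses laboratory values already collected.

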#### 6.7.3. Vital Signs

#### Definition

Vital sign parameters to be summarized include body temperature [°C], pulse rate [bpm], respiratory rate [breaths per minute], and systolic and diastolic blood pressure [mmHg] and will be assessed at the time-points indicated in Table 5, 6 and 7 of the protocol. Only body temperature assessed at the vital signs assessments will be shown (no body temperature assessed in the diary). Normal ranges of the vital sign parameters are given in Table 3. If a value is out of range, it is categorized as CS or not clinically significant (NCS) in the CRF.

Parameter	Range
Systolic blood pressure	90-140 mmHg
Diastolic blood pressure	<= 90 mmHg
Pulse rate	50-100 bpm
Respiration rate	8-20 breaths per minute
Temperature (where applicable)	35.5-37.5 °С

#### Table 3 Normal Ranges for Vital Signs

#### Analysis

Vital sign variables at each time-point, and its change from baseline to each post-baseline timepoint will be summarized using descriptive summary statistics for each parameter by group and cohort-total.

Vital sign values for each parameter will be classified as normal/abnormal according to whether the value is within or outside of the reference range for that parameter (see Table 3). The number and percentage of subjects with CS abnormal, abnormal (not CS), normal and missing values will be summarized for each parameter by group and cohort-total.

All vital sign data will be presented in the data listings. Abnormal vital signs values and clinically significant vital sign abnormalities will be flagged in the listing.

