### 2.3.1 Risk assessment

The risks linked to the trial-specific procedures and connected mitigations are as follows:

- The volume of blood drawn will be kept to a minimum and will remain less than that drawn when donating blood:
  - For subjects in Cohorts 1 to 10, up to approximately 592 mL blood will be drawn per subject over the complete trial, i.e., over approximately 223 d.
  - For subjects in Cohorts 11 to 13, up to approximately 1,025 mL blood will be drawn per subject over the complete trial, i.e., over approximately 760 d.
  - For subjects in Cohort 14, up to approximately 477 mL blood will be drawn per subject over the complete trial, i.e., over approximately 223 d.
- All trial-specific procedures will be performed by qualified trial site personnel.
- Immunization will be done by a physician.
- Human experience with BNT162 vaccines was not available prior to this trial. However, clinical data was available for RNAs formulated with related but not identical liposomal compositions or non-formulated RNAs and can support risk assessment of the BNT162 vaccines.

Based on such data, the risks linked to the immunization with the BNT162 vaccines are as follows:

- Due to the IM route of administration, there is the risk of local reactions at the injection site, e.g., erythema, pruritus, pain, tenderness, swelling, sweating.
- Due to their immune-modulatory effect, vaccines may cause systemic flu-like reactions such as temporary headache, fatigue, loss of appetite, myalgia, arthralgia, fever. Rarely, with certain prophylactic vaccines (e.g., as seen for vaccines using attenuated viruses) severe allergic reaction or a neurological side effects, such as a seizure, were seen. Although these rare side effects are a concern, the risk of a vaccine causing serious harm or death is considered to be extremely small, in particular for BNT162 vaccines, which are molecularly defined, highly purified and based on RNA, which naturally occurs and is metabolized in the human organism.
- Due to the IM route the risk of systemic reactions is considered low.

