### 6.6.1 Dose limiting toxicity

### Applicable to dose ranging cohorts only

During the time of enrollment into a given dose escalation cohort in Part A, if any of the following events occur, it will be considered an individual dose limiting toxicity and further dosing in that cohort will be stopped:

- Anaphylactic reaction considered related.
- Generalized urticaria considered related.
- Four trial subjects in that cohort with any severe unsolicited local event, if considered related and not manageable with simple measures (e.g., cooling, analgesia, nonsteroidal anti-inflammatory drugs [NSAIDs]).
- AEs within 7 d of vaccination assessed by the investigator to be potentially lifethreatening (Grade 4) and that are possibly related, or for which there is no alternative, plausible, attributable cause.
- Any systemic SAE within 7 d of vaccination that is assessed by the investigator as possibly related, or for which there is no alternative, plausible, attributable cause.
- Any fever >40.0°C (>104.0°F) within 7 d of vaccination considered related and confirmed by an investigator or medically qualified person.
- Two trial subjects (at any dose level) with the same or similar severe (Grade 3 or higher) AE (including reactogenicity reported as AEs and clinically significant laboratory abnormalities) within 7 d of vaccination, considered related, or for which there is no alternative, plausible, attributable cause (for severity grading of AEs see Section 10.3.1.7).

Page 66 of 113 Version: 13.0 Date: 12 JAN 2022

For the cohorts with BNT162c2 P/B dosing, dosing with the boost dose will only start after SRC assessment of Day 28 safety data (solicited and unsolicited) for the cohort testing BNT162c2 (SD).

Approval from the SRC will be required prior to any further dosing in the affected cohort. The SRC may call for the opening of a lower dose level cohort.

The same events will prompt IMP discontinuation for individual subjects as described in Section 6.6.4. Tasks connected to the discontinuation of IMP are described in Section 7.1.

The above guidance regulates how potential dose limiting toxicities may influence the decisions to further enroll trial subjects in any cohort. These decisions are taken by the SRC based on the 48 h safety data from the first 6 subjects of each cohort (see Section 4.1). Due to the staggered sentinel dosing design, subjects will have been followed for 4 d for the sentinel subjects when this SRC decision is made.

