## 6.1.1. Tables and Listings

#### Tables

In general, data will be summarized by groups (i.e., by vaccine type [BNT162a1, BNT162b1, BNT162b2, BNT162c2 SD and BNT162c2 P/B] and cohort) and all cohorts combined for each type (cohort-total). Furthermore, selected cohorts may be combined. The cohorts and cohort-total will be presented in columns and the different vaccine types in different tables.

There may be additional total columns for younger (18 to 55 years) and older (56 to 85 years) subjects.

Descriptive summary tables as well as figures will be based on scheduled visits.

Continuous variables will be summarized by group using the following descriptive statistics: number of subjects with non-missing data (n), mean, standard deviation (SD), median, minimum (min) and maximum (max).

Descriptive statistics of titer and fold increase of titer will additionally include geometric mean and its two-sided 95% confidence interval (CI). The geometric mean titer (GMT) is calculated as the mean of the logarithm of the functional antibody titers, back-transformed into the original scale. Two-sided CIs will be obtained by calculating CIs using t-distribution for the mean of the logarithmically transformed assay results and transforming the limits back to the original scale.

Geometric mean fold rise (GMFR) is calculated as the mean of the difference of logarithmically transformed assay results (post vaccination time point – pre vaccination time point) and back-transformed into the original scale. Two-sided CIs will be obtained by calculating CIs using Student's t-distribution for the mean difference of the logarithmically transformed assay results and transforming the limits back to the original scale.

Categorical variables will be summarized by group presenting absolute and relative frequencies (n and %) of subjects in each category (including the category 'missing' if applicable).

Percentages will be calculated based on the number of subjects in the respective analysis set (N) as denominator if not stated differently. Percentages may be presented with exact 95% Clopper-Pearson CIs.

SDs as well as CIs will only be calculated if values of at least 3 subjects are available.

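### SAP 6.7.3 gives no count of subjects with low vital signs: diastolic pressure has no lower limit, and for the other parameters low and high values are added together

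*SAP*

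**What the plan says.** SAP 6.7.3 sets normal ranges for five vital signs in its Table 3. Systolic pressure (90 to 140 mmHg), pulse (50 to 100 bpm), respiration (8 to 20 breaths per minute) and temperature (35.5 to 37.5 °C) each have a lower and an upper limit. Diastolic pressure has an upper limit of 90 mmHg and no lower one.

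The ranges drive two steps. At data collection: "If a value is out of range, it is categorized as CS or not clinically significant (NCS) in the CRF". In the analysis: "Vital sign values for each parameter will be classified as normal/abnormal according to whether the value is within or outside of the reference range". The categorical table follows from both: "The number and percentage of subjects with CS abnormal, abnormal (not CS), normal and missing values will be summarized for each parameter", by group and for all cohorts of a vaccine together. Abnormal and clinically significant values are also flagged in the listing.

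Two other outputs are planned. One is continuous: "Vital sign variables at each time-point, and its change from baseline to each post-baseline timepoint will be summarized using descriptive summary statistics". SAP 6.1.1 puts minimum and maximum among those statistics. The other is the listing: "All vital sign data will be presented in the data listings".

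Protocol Tables 6 to 9 schedule vital signs before dosing, at 1, 3 and 6 h after each immunization, and at later visits.

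**The concern.** The primary objective is to describe safety and tolerability. Protocol 2.3.1 notes that, rarely and with certain prophylactic vaccines, "severe allergic reaction or a neurological side effects, such as a seizure, were seen". The first dose-limiting event in protocol 6.6.1 is "Anaphylactic reaction considered related". A reader of the safety tables can therefore reasonably ask how many subjects had a low blood pressure in the hours after a dose.

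The categorical table is the only vital-sign output in the SAP that counts subjects, and it cannot answer that question. For diastolic pressure, low values fall in the normal row. For the other four parameters, they are added to high values. The SAP also leaves open whether a subject is placed in a category by the reading at each visit, by the worst reading or by some other rule. For laboratory values, SAP 6.7.2 does plan a count of low, normal and high at each time point, and shift tables that look in both directions.

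**Working it through.** There is no stated figure to reproduce: this part of the plan is descriptive, with no test, power or margin. The check applies the Table 3 ranges as a rule.

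**Rule.** Systolic is normal if 90 ≤ value ≤ 140. Diastolic is normal if value ≤ 90. Anything else is abnormal.

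**Applied to illustrative readings** (chosen for the check, not trial data):

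| Reading (mmHg) | Systolic | Diastolic |
|---|---|---|
| 120/75 | normal | normal |
| 110/40 | normal | normal |
| 95/35 | normal | normal |
| 80/40 | abnormal | normal |
| 85/55 | abnormal | normal |
| 160/85 | abnormal | normal |
| 160/100 | abnormal | abnormal |
| 120/95 | normal | abnormal |

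Three results follow.

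1. Every diastolic value from 0 to 90 is normal. The number of low diastolic values the table can show is 0 in every cohort, whatever the data. An abnormal diastolic value can only be a high one.
2. 80/40 and 160/85 fall in the same pair of cells if the clinical-significance judgement is the same.
3. Systolic values below 90 are classed as abnormal, not as normal.

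**Effect of adding low and high together.** Assume a cohort of 12 with 4 subjects above 140 mmHg and 1 below 90 mmHg at one time point. The table shows 4 + 1 = 5 abnormal, 5/12 = 42%. The low count is 1/12 = 8%. Read in reverse, 5 abnormal of 12 fits any low count from 0 (0%) to 5 (42%). If the minimum at that time point is below 90 and the maximum above 140, at least one subject lies on each side. The low count is then between 1 (8%) and 4 (33%), so the continuous summary narrows the range but does not close it.

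**Time points.** Under protocol Table 6 a prime/boost subject has up to 16 vital-sign readings: 2 before any dose (Visit 0 and Visit 1 pre-dose), 6 at 1, 3 and 6 h after the two doses, and 8 others (Visits 2 and 3, Visit 4 pre-dose, and Visits 5 to 9); 2 + 6 + 8 = 16. The continuous summary is specified for each time point. The sentence on the categorical table names the parameter and the group, but no time point and no rule for choosing among readings.

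**Comparison with SAP 6.7.2.** The laboratory section has a table by clinical significance in nearly the same words, also without direction or time point. It adds low/normal/high counts at each time point and shift tables. The difference is that vital signs lack this additional output.

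**The case against.** The strongest reply is that little is hidden. Systolic pressure below 90 mmHg is out of range, is judged for clinical significance and is flagged. Minima and changes from baseline at each time point show low values. All readings are listed, and in cohorts of 12 the direction can be read subject by subject. Protocol 10.3.1.1 and 10.3.1.9 let a vital-sign abnormality that the investigator judges clinically significant lead to an adverse-event record, without tying that judgement to SAP Table 3. Related anaphylaxis is a dose-limiting event reported within 24 h. The Safety Review Committee sees vital signs of the first six subjects in escalation cohorts. SAP 6.4.3 counts subjects with dose-limiting, serious and Grade 3 or higher events. All of this stands. It shows that the data survive and that serious events have their own routes. It does not supply a count of subjects with low values, and a low diastolic value in the listing would carry no out-of-range flag.

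A reader might infer more than the documents support:

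- **That hypotension as such is counted as normal or cannot be told from hypertension.** This fails for the reasons above; the gap lies in one table and in the flags.
- **That screening and post-dose readings are pooled in one cell.** The SAP is silent on the time point. SAP 6.1.1 says summary tables use scheduled visits, and the table layouts are not in the documents.
- **That the post-dose readings exist to detect anaphylaxis.** The risk and dose-limiting-toxicity passages do not mention blood pressure, and the risk section calls the chance of serious harm extremely small.
- **That high readings swamp low ones in the older cohorts.** No data are given, and uncontrolled hypertension is an exclusion criterion for older volunteers.

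**Conclusion.** The point holds as a reporting gap. As written, SAP 6.7.3 makes the count of low diastolic values zero by construction, leaves such values unflagged, merges low with high for the other four vital signs, and does not say which reading is counted. No planned vital-sign output gives the number of subjects with a low value after dosing.

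The size is limited. This is one descriptive table under further safety analyses. No endpoint, test or dose-escalation rule depends on it, and the readings remain available. The 12-subject example rests on assumed counts and shows only how much the merged figure can leave open.

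The verdict assumes that Table 3 is applied literally and is the range behind the CRF's out-of-range step. The CRF itself is not in the documents, so whether low diastolic values were in fact judged for clinical significance is unknown.

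**What to change.** 1. State whether the one-sided diastolic range is intended. If it is not, the sponsor should supply the lower limit from its own source; the documents give none and none is proposed here. Either way, reconcile Table 3 with the CRF step that triggers the clinical-significance judgement.
2. Add to SAP 6.7.3 a count and percentage of subjects low, normal and high for each vital sign at each scheduled time point, including 1, 3 and 6 h after each dose, as SAP 6.7.2 does for laboratory values.
3. Keep the existing table by clinical significance, and say which time point or reading places a subject in a category.
4. While editing, correct the cross-reference. The section points to protocol Tables 5, 6 and 7, but Table 5 gives subject numbers and the schedules for Cohorts 11 to 14 are in Tables 8 and 9.

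No new data are needed. The cost is SAP wording and one more table. If a lower diastolic limit is added, any low diastolic values without a recorded clinical-significance judgement would have to be shown as unclassified.
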